#### 9.1.4. Population of Interest

The primary PK analyses will be based on the PK Population, unless otherwise specified.

## 10. BIOMARKER ANALYSES

Biomarker data is being collected, but there will be no biomarker analyses conducted.

## 11. POPULATION PHARMACOKINETIC (POPPK) ANALYSES

No POPPK analyses will be conducted.

## 12. PHARMACOKINETIC / PHARMACODYNAMIC ANALYSES

No pharmacokinetic/pharmacodynamic analyses will be conducted.

## **14. APPENDICES**

### **14.1. Appendix 1: Protocol Deviation Management and Definitions for Per Protocol Population**

#### **14.1.1. Exclusions from Per Protocol Population**

No Per Protocol population is defined and used for this study.

**14.2. Appendix 2: Schedule of Activities**

**14.2.1. Protocol Defined Schedule of Events**

Refer to Protocol Section 1.3.

**14.3. Appendix 3: Assessment Windows**

No assessment window will be applied.

## 14.4. Appendix 4: Study Phases and Treatment Emergent Adverse Events

### 14.4.1. Study Phases

#### 14.4.1.1. Study Phases for Concomitant Medication

| Study Phase | Definition   |
|-------------|--|
| Prior       | 

Medication End Date < Study Treatment Start Date

                          |
| Concomitant | 

Study Treatment Start Date ≤ Medication End Date ≤ Study Treatment Stop Date

 |

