## **5.8. Other Considerations for Data Analyses and Data Handling Conventions**

Other considerations for data analyses and data handling conventions are outlined in the appendices:

| Section | Component   |
|----------------|--|
| 14.3           | Appendix 3: Assessment Windows                                 |
| 14.4           | Appendix 4: Study Phases and Treatment Emergent Adverse Events |
| 14.5           | Appendix 5: Data Display Standards & Handling Conventions  |
| 14.6           | Appendix 6: Derived and Transformed Data                       |
| 14.7           | Appendix 7: Reporting Standards for Missing Data               |
| 14.8           | Appendix 8: Values of Potential Clinical Importance            |

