## **6.5. Concomitant Medications**

All concomitant medications will be summarized. Concomitant medications will be coded using GSK Drug coding dictionary and summarized. The summary of concomitant medications will show the number and percentage of participants taking concomitant medication by Ingredient. Multi-ingredient products will be summarized by their separate ingredients rather than as a combination of ingredients. Anatomical Therapeutic Chemical (ATC) classification Level 1 (Body System) information will be included in the dataset created but will not appear in the summary.

In the summary of concomitant medications, each participant is counted once within each unique ingredient. For example, if a participant takes Amoxicillin on two separate occasions, the participant is counted only once under the ingredient 'Amoxicillin'. In the summary of concomitant medications, the ingredients will be summarized by the base only.

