**NOTES:**

- Please refer to [Appendix 7: Reporting Standards for Missing Data](#) for handling of partially missing dates for concomitant medication.

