#### 14.7.2.1. Handling of Missing and Partial Dates

| Element        | Reporting Detail  |
|----------------|---|
| General        | 
 
• Partial dates will be displayed as captured in subject listing displays. However, where necessary, display macros may impute dates as temporary variables for sorting data in listings only. In addition, partial dates may be imputed for ‘slotting’ data to study phases or for specific analysis purposes as outlined below.
 
   |
| Adverse Events | 
 
• Imputations in the adverse events dataset are used for slotting events to the appropriate study time periods and for sorting in data listings.
 
• The eCRF allows for the possibility of partial dates (e.g., only month and year) to be recorded for AE start and end dates; that is, the day of the month may be missing. In such a case, the following conventions will be applied for calculating the time to onset and the duration of the event:               
 
○ Missing Start Day: 
 
▪ If study treatment start date is missing (i.e. participant did not start study treatment), then set AE start date = 1st of month.
 
▪ Else if study treatment start date is not missing:
If month and year of AE start date = month and year of study treatment start date then
 
 
 
 
 
 |

| Element                 | Reporting Detail  |
|-------------------------|---|

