| Concomitant Medications | 
 
• Completely missing start dates will not be imputed
 
• Partial start dates for any concomitant medications recorded in the CRF will be imputed using the following convention:             
 
○ If day and month are missing:                 
 
– If treatment start date is missing (i.e., subject did not start study treatment), a '01' will be used for the day and 'Jan' will be used for the month;
 
– If treatment start date is not missing                     
 
▪ If year of start date = year of study treatment start date                             
 
· If stop date contains a full date which is earlier than the treatment start date, a '01' will be used for the day and 'Jan' will be used for the month;
 
· else study treatment start date will be used
 
 
 
▪ else a '01' will be used for the day and 'Jan' will be used for the month
 
 
 
 
 
○ If day is missing:                 
 
– If treatment start date is missing (i.e., subject did not start study treatment), a '01' will be used for the day;
 
– If treatment start date is not missing                     
 
▪ If year and month of start date = year and month of study treatment start date                             
 
· If stop date contains a full date which is earlier than the treatment start date, a '01' will be used for the day;
 
· else study treatment start date will be used
 
 
 
▪ else a '01' will be used for the day and 'Jan' will be used for the month
 
 
 
 
 
 
 
• Completing missing end dates will not be imputed
 
• Partial end dates for any concomitant medications recorded in the CRF will be imputed using the following convention:             
 
○ If day and month are missing                 
 
– Earliest of (Dec 31st, date of last contact) will be used
 
 
 
 
 
 |

| Element   | Reporting Detail   |
|---|--|

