|   | 
 
○ If day is missing               
 
– Earliest of (last day of the month, date of last contact) will be used
 
 
 
  |
| New Anti-Cancer Therapy/
Radiotherapy/
Surgical Procedures for Efficacy Evaluation (e.g., response rate, time to event) | 
Start dates for follow-up anti-cancer therapy, radiotherapy, and surgical procedures will be imputed in order to define event and censoring rules for progression-free survival, response rate, or duration of response (i.e. start date for new anti-cancer therapy). Dates will only be imputed when a month and year are available but the day is missing. The following rules will be used to impute the date when partial start dates are present on anti-cancer therapy, radiotherapy, and/or surgical procedures dataset[s]:
 
 
• Completely missing start dates will remain missing, with no imputation applied;
 
• Partial start dates will be imputed using the following convention:               
 
• If both month and day are missing, no imputation will be applied;
 
• If only day is missing:                   
 
○ If the month of partial date is the same as the month of last dosing date, minimum of (last dosing date + 1, last day of the month) will be used for the day;
 
○ If the month of partial date is the same as the month of last disease assessment and the last disease assessment is PD, minimum of (last date of disease assessment + 1, last day of the month) will be used for the day;
 
○ If both conditions above are met, the later date will be used for the day;
 
○ Otherwise, a '01' will be used for the day;
 
 
 
 
 
• Completely or partial missing end dates will remain missing, with no imputation applied;
 
 |

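### The SAP assigns medication phase from the end date alone, so a drug taken on treatment that outlasts the last dose, or has no end date, is neither prior nor concomitant

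*SAP*

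**What the plan says.** SAP 14.4.1.1 has two medication phases. A medication is prior if its end date is before the treatment start date. It is concomitant if "Study Treatment Start Date ≤ Medication End Date ≤ Study Treatment Stop Date". There is no ongoing category and no post-treatment category. The note under that table refers to Appendix 7 "for handling of partially missing dates for concomitant medication".

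Appendix 7 (SAP 14.7.2.1) says in its general row that partial dates may be imputed to slot "data to study phases or for specific analysis purposes as outlined below". For concomitant medications it then says:

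- on absent end dates, "Completing missing end dates will not be imputed";
- on absent start dates, "Completely missing start dates will not be imputed";
- on end dates lacking only the day, "Earliest of (last day of the month, date of last contact) will be used";
- on end dates lacking day and month, the earlier of 31 December and last contact is used.

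None of these is capped at the last dose.

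SAP 6.5 states that "All concomitant medications will be summarized" and gives no definition of its own. SAP 5.8 says that "Other considerations for data analyses and data handling conventions are outlined in the appendices", and lists Appendix 4, which holds the phase table. Protocol 6.7 requires recording of drugs being taken at enrolment, on study intervention, and for 30 days after the last dose, with start and end dates.

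**The concern.** Whether a drug was concomitant depends on whether it was taken while the participant was on treatment. That needs both dates. The SAP's rule instead asks whether the drug was stopped while the participant was on treatment. A drug started before or during dosing and continued past the last dose fails the test, and so does one recorded as ongoing.

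Such records are foreseeable, because Protocol 6.7 collects drugs for 30 days beyond the last dose. That section also allows prophylactic low molecular weight heparin and Factor Xa inhibitors, in a study whose enrolment was paused for thromboembolic events. An anticoagulant taken throughout treatment and continued afterwards would have no phase.

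Table 1.12 (SAP 14.10.3) is the only planned summary table of medications, and no prior-medication table is planned. If the phase is applied, a record in neither phase reaches no summary table, contrary to SAP 6.5.

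**Working it through.** The plan gives no figure to reproduce, so the check applies the written rule to every kind of record.

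**Inputs.** Let S and T be treatment start and stop, and B and E the medication start and end. From SAP 14.4.1.1:

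- prior: E < S
- concomitant: S ≤ E ≤ T

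From SAP 14.7.2.1, a completely missing E stays missing.

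**Patterns.** B and E can each be before, during or after treatment, or missing: 4 × 4 = 16 combinations. Three are impossible because the end precedes the start (during/before, after/before, after/during), leaving 16 − 3 = 13. Two have an end before treatment and are prior (before/before, missing/before). Two have a known start after the last dose (after/after, after/missing). The other 13 − 2 − 2 = 9 are:

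| Start | End | Overlaps treatment? | SAP rule | Overlap rule |
|---|---|---|---|---|
| before | during | certainly | concomitant | concomitant |
| during | during | certainly | concomitant | concomitant |
| missing | during | certainly | concomitant | concomitant |
| before | after | certainly | neither | concomitant |
| during | after | certainly | neither | concomitant |
| during | missing | certainly | neither | concomitant |
| before | missing | possibly | neither | concomitant |
| missing | after | possibly | neither | concomitant |
| missing | missing | possibly | neither | concomitant |

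The overlap rule is (B ≤ T or B missing) and (E ≥ S or E missing). The SAP rule gives 3 of 9, and 3 of the 6 certain cases. The overlap rule gives 9 of 9 and 6 of 6, and adds none of the other four patterns. The missing-start clause is needed: without it the overlap rule would lose missing/during, which the SAP now keeps.

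**Partial end dates.** Assume a last dose on 10 June 2019 and last contact on 10 July 2019.

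- End recorded as June 2019: min(30 June, 10 July) = 30 June, after the last dose, so neither.
- End recorded as 2019: min(31 December, 10 July) = 10 July, after the last dose, so neither.

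More generally, take an end date with the day missing in the month of the last dose, and any contact after the last dose. The imputed end falls after the last dose unless the last dose was on the final day of the month: 365 − 12 = 353 of 365 possible last-dose dates. If last contact was the last-dose date, it is 0 of 365. This shows how the rule behaves and does not estimate how often the situation arises.

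**The case against.** The strongest objection is that the loss of records is conditional. SAP 6.5 does not cite Appendix 4, Table 1.12 has no programming note applying the phase, and SAP 6.1 and 14.5.2 rely on sponsor display standards that are not in the documents and may handle ongoing drugs. That stands as a limit on the consequence. It does not rescue the rule, which is the SAP's only definition of concomitant and sits in an appendix that SAP 5.8 names for data handling. If the phase is not used, section 6.5 has no operational definition.

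Three further points have some force:

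- SAS, the stated software, orders a missing value below any date, so a literal program could label an ongoing drug prior instead of leaving it unclassified. That changes the error without removing it.
- SAP 6.5 counts a participant once per ingredient, so a dropped record alters the table only if no other record for that ingredient qualifies. The effect on table counts may therefore be smaller than the effect on records.
- The three uncertain patterns could include drugs that were truly prior or post-treatment. Counting them as concomitant is a cautious convention, not a proven classification.

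Listing 8 is also planned for the final analysis with no stated phase filter, so the records may still be visible there. Its own programming note, however, says the listing is unnecessary when a table is produced.

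**Conclusion.** The concern holds. As written, the rule leaves without a phase any medication taken on treatment that ended after the last dose. It does the same to one with no end date, or with a partial end date imputed past the last dose. No other section repairs this. Of the six patterns that certainly overlap treatment, three are missed; of nine that do or may overlap, six are missed.

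The number of records affected cannot be computed from the documents, and the pattern counts are not weighted by how common each pattern is. Omission from Table 1.12 assumes that the table is built from this phase. The consequence is confined to a descriptive summary; the dose-limiting toxicity, adverse event, best response and pharmacokinetic analyses do not use the phase. The definition should be corrected, but the study's conclusions do not depend on it.

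**What to change.** Replace the concomitant definition in SAP 14.4.1.1 with: medication start on or before treatment stop, or start date missing; and medication end on or after treatment start, or ongoing, or end date missing. Keep the prior definition. Exclude from concomitant any drug known to have started after treatment stop; a separate post-treatment display for these is optional. State in SAP 6.5 that Table 1.12 uses this phase.

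One consequential correction is needed because the new rule uses start dates. In SAP 14.7.2.1, when only the start day is missing and the start month and year differ from those of treatment start, the rule replaces the recorded month with January. For example, with treatment from April to 10 June 2019, a drug started in August 2019 would be imputed to 1 January 2019 and wrongly counted as concomitant. That branch should set the day to 01 and keep the recorded month.

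The cost is a few lines of SAP text, one derivation change and a re-run of Table 1.12. Data collection does not change, because Protocol 6.7 already requires both dates.

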**NOTES:**

- Please refer to [Appendix 7: Reporting Standards for Missing Data](#) for handling of partially missing dates for concomitant medication.

## 14.5. Appendix 5: Data Display Standards & Handling Conventions

### 14.5.1. Reporting Process

|   |                        |
|---|------------------------|
| Software   |                        |
| 
 
The currently supported versions of SAS software TSCG will be used.
 
   |                        |
| Reporting Area   |                        |
| HARP Server   | : US1SALX00259         |
| HARP Compound   | : gsk3368715\mid207675 |
| Analysis Datasets  |                        |
| 
 
Analysis datasets will be created according to CDISC standards (SDTM IG Version 3.2 & ADaM IG Version 1.1).
 
 |                        |
| Generation of RTF Files  |                        |
| 
 
RTF files will be generated upon request.
 
   |                        |

### 14.5.2. Reporting Standards

|   |  |
|---|--|
| General  |  |
| 
 
The current GSK Integrated Data Standards Library (IDSL) will be applied for reporting, unless otherwise stated (IDSL Standards Location: https://spope.gsk.com/sites/IDSLLibrary/SitePages/Home.aspx): 
 
4.03 to 4.23: General Principles
 
5.01 to 5.08: Principles Related to Data Listings
 
6.01 to 6.11: Principles Related to Summary Tables
 
7.01 to 7.13: Principles Related to Graphics
 
 
 
  |  |
| Formats  |  |
| 
 
GSK IDSL Statistical Principles (5.03 & 6.06.3) for decimal places (DP's) will be adopted for reporting of data based on the raw data collected, unless otherwise stated.
 
Numeric data will be reported at the precision collected on the eCRF.
 
The reported precision from non eCRF sources will follow the IDSL statistical principles but may be adjusted to a clinically interpretable number of DP's.
 
  |  |
| Planned and Actual Time  |  |
| 
 
Reporting for tables, figures and formal statistical analyses: 
 
Planned time relative to dosing will be used in figures, summaries, statistical analyses and calculation of any derived parameters, unless otherwise stated.
 
The impact of any major deviation from the planned assessment times and/or scheduled visit days on the analyses and interpretation of the results will be assessed as appropriate.
 
 
 
Reporting for Data Listings: 
 
Planned and actual time relative to study drug dosing will be shown in listings (Refer to IDSL Statistical Principle 5.05.1).
 
Unscheduled or unplanned readings will be presented within the subject's listings.
 
 
 
 |  |
| Unscheduled Visits   |  |
| 
 
Unscheduled visits will not be included in summary tables, except in cases where worst-case post-baseline is calculated.
 
Unscheduled visits will not be included in figures, unless otherwise specified.
 
All unscheduled visits will be included in listings.
 
   |  |

| Descriptive Summary Statistics   |  |
|--|--|
| Continuous Data  | Refer to IDSL Statistical Principle 6.06.1 |
| Categorical Data   | N, n, frequency, %                         |
| Graphical Displays   |  |
| 
 
Refer to IDSL Statistical Principals 7.01 to 7.13.
 
 |  |

### 14.5.3. Reporting Standards for Pharmacokinetic

| Pharmacokinetic Concentration Data                              |   |
|---|---|
| PC Windows Non-Linear (WNL) File                                | 
PC WNL file (CSV format) for the non-compartmental analysis by Clinical Pharmacology Modelling and Simulation function will be created according to SOP_00000314000: Non-compartmental Analysis of Clinical Pharmacokinetic Data.
 
Note: Concentration values will be imputed as per GUI_51487.
   |
| ADPC data file  | 
To create ADPC the SDTM PC domain dataset will be merged with the Subject-Level Analysis Dataset (to get demographic information) and with SDTM EX domain (to get reference timepoint date).
 
Reference timepoint date will be populated for both study drug and active metabolite based on study treatment information from SDTM EX domain.
 
To populate analysis values in ADPC (AVAL(C)) adjustments to the PCSTRESN will be done based on imputation rules from "Non-Compartmental Analysis of Pharmacokinetic Data, CPMS Global" document.
 
Total Moiety parameter will be added, along with concentrations of study drug and active metabolite, and derived as the sum of study drug and active metabolite concentrations converted to nM units.
 |
| Descriptive Summary Statistics, Graphical Displays and Listings | 
Refer to IDSL PK Display Standards.
 
Refer to IDSL Statistical Principle 6.06.1.
 
Note: Concentration values will be imputed as per GUI_51487 for descriptive summary statistics/analysis and summarised graphical displays only. Assign zero to NQ values.
   |
| Pharmacokinetic Parameter Derivation                            |   |
| PK Parameters to be Derived by PK Programmer                    | The following PK parameters will be derived by the Programmer: $C_{max}$ , $T_{max}$ , and $C_{\tau}$ .   |
| Pharmacokinetic Parameter Data                                  |   |
| Is NQ impacted PK Parameters Rule Being Followed                | Yes. Refer to Standards for Handling NQ Impacted PK Parameters.   |

## 14.6. Appendix 6: Derived and Transformed Data

### 14.6.1. General

|  |
|--|
| 
Multiple Measurements at One Analysis Time Point
 
 
• Mean of the measurements will be calculated and used in any derivation of summary statistics but if listed, all data will be presented.
 
• If multiple assessments on different days are reported for the same scheduled assessment, then the worst-case assessment for that scheduled assessment will be analysed.
 
• Participants having both High and Low values for Normal Ranges at any post-baseline visit for safety parameters will be counted in both the High and Low categories of “Any visit post-baseline” row of related summary tables. This will also be applicable to relevant Potential Clinical Importance summary tables.
 
 |
| 
Study Day
 
 
• Calculated as the number of days from First Dose Date: 
 
○ Ref Date = Missing → Study Day = Missing
 
○ Ref Date < First Dose Date → Study Day = Ref Date – First Dose Date
 
○ Ref Date ≥ First Dose Date → Study Day = Ref Date – (First Dose Date) + 1
 
 
 
  |
| 
Change from Baseline
 
 
• Change from Baseline = Post-Baseline Visit Value – Baseline
 
• % Change from Baseline = 100 x (Post-Baseline Visit Value – Baseline) / Baseline
 
• If either the Baseline or Post-Baseline Visit Value is missing, Change from Baseline and % Change from Baseline is set to missing
 
  |
| 
Date of Response
 
 
• For post-baseline disease assessments, the date of response (PR or CR) is assigned to the latest date of disease assessment; for other response categories (SD, NE, PD), the date of response is assigned to the earliest date of disease assessments.
 
  |
| 
Date of New Anti-Cancer Therapy
 
 
• Derived as the earliest date of new anti-cancer systemic therapy, radiotherapy or cancer-related surgical procedure.
 
• Missing or partial dates will be imputed for derivation of new anti-cancer therapy following rules specified in Section 14.7.2.1.
 
  |

### 14.6.2. Study Population

|  |
|--|
| 
Extent of Exposure
 
 
• Missing treatment stop date will be imputed following rules specified in Section 14.7.2.1.
 
• Daily Oral Drugs 
 
○ Number of days of exposure (duration on study treatment) to study drug will be calculated based on the formula: 
Duration of Exposure in Days = Treatment Stop Date – Treatment Start Date + 1
 
 
○ Participants who were enrolled but did not report a treatment start date will be categorized as having zero days of exposure.
 
○ The cumulative dose will be based on the formula: 
Cumulative Dose = Sum of (Number of Days x Total Daily Dose)
 
 
○ If there are any treatment breaks during the study, exposure data will be adjusted accordingly.
 
 
 
 |
|--|

| Time since Initial Diagnosis   |
|---|
| 
 
• Calculated as the number of days from the Date of Initial Diagnosis:               
 
○ If First Dose Date is missing → Elapse Time = Missing
 
○ If Date of Initial Diagnosis is completely/partially missing → Elapse Time = Missing
 
○ Otherwise → Elapse Time = First Dose Date – Date of Initial Diagnosis + 1
 
 
 
• To report in months, divide the number of days by 30.4375; to report in weeks divide the number of days by 7; to report in years divide the number of days by 365.25.
 
 |

